After training, the task will begin. A reward (portion of food or access to music) will be presented after the infant meets the response criteria. The schedules will begin with one button press to earn a reward, and will increase linearly every two trials, up to a maximum of 15 responses (i.e., 1,1,2,2,3,3,...,15,15). The number of responses, number of rewards earned, and time spent in each session will be recorded. When food is earned during the task, the researcher will place a piece of the infant’s favorite solid food (approximately 1 cm x 1 cm x 1 cm) in front of them. When the non-food alternative is earned, researchers will play a song for approximately 10 seconds. Infants will work for access to the food or music in a counterbalanced order. Infants will continue the task until they give signs of wanting to stop (e.g., crying, signing or saying ‘all done’, head turning away, etc.). The session will end when the infant no longer wishes to earn points for access to food or music or he/she fusses or cries for more than 60 seconds. The total amount of food consumed by the infant will be measured and recorded at the end of visit, including the total amount of food removed from the infant’s tray during the reinforcement task.

The dependent measure is a standard measure of reinforcing value, operationalized by Pmax, or the highest schedule requirement the infant completes to earn a food or non-food alternative. To assess the ratio of reinforcing value of food to alternatives, or the FRR, we will assess the proportion of responding for food [$P_{max\ food}/(P_{max\ food} + P_{max\ non-food\ alternative})$]. Pmax can be positively skewed, and if not normally distributed, the natural log of Pmax will be used as the primary dependent variable. Infants will be defined as high in food reinforcement at baseline if they choose to allocate more effort to obtain food than the alternative behaviors being studied ($FRR\ [P_{max\ food}/(P_{max\ food} + P_{max\ non-food\ alternative})] > 0.5$). Each child will be tested for the FRR of food versus music.

f) Infant Diet and Energy intake

We will measure child diet and energy intake with three 24-hour dietary recalls (2 weekdays and 1 weekend) via telephone using a modified approach from the Feeding Infants and Toddlers Study. Information on the time, type, brief description (i.e., brand name, preparation, additives), and amount of each food or beverage consumed by the child from midnight

through midnight on the previous day will be collected from the participating parent (or the most knowledgeable adult). The participating parent will receive a booklet with drawings of cups, bowls, jars, and spoons to assist him/her to recall the actual amount of foods and drinks consumed, excluding spillover or leftover by the infant. The dietary recalls should include foods and drinks fed by parents at home and also by other caregivers (i.e., daycare) if applicable. Infant use of vitamin and mineral supplements will be recorded. We plan to use the nutrient analysis software Nutritionist Pro or NDSR to enter and analyze data collected from the 24-hour recalls. Food and nutrient analyses can be conducted at the ingredient-, food-, meal-, or daily total level. For breastfed infants, interviewers will document the duration of each feeding in minutes. For infants 7 months and older, we will assume an intake of 600 mL per day as the quantity of breast milk for those being fed only breast milk. The volume of formula or cow's milk will be subtracted from 600 mL for infants who consume both breast milk and other milk products to estimate the quantity of breast milk consumed. A dietetics professional will review all 24-hour recalls for missing foods, unrealistic quantities reported, supplement use, including brand name and type, and breastfeeding status. Nutrient calculations will be performed using the Nutritionist Pro Software or NDSR software. We will calculate the average daily energy intake by averaging the three 24-hour energy intakes, which has been shown to be an optimal method for estimating energy intake.

g) Infant Toddler- Home Observational Measurement of Environment (IT-HOME)

The quality of the home environment will be assessed using a modified for laboratory visits infant-toddler questionnaire/observational version of the HOME Inventory during the lab visits. Meta-analysis has shown that a positive parent-child relationship among children and adolescents and higher levels of parental responsiveness assessed by the IT-HOME were associated with lower weight, healthier eating, and more physical activity of the child. The HOME Inventory is a widely used and well-validated measure of the home environment, using both direct observation and parental interview. The infant-toddler version of the HOME Inventory consists of a set of 45 binary items describing eight dimensions of the home environment yielding eight separate sub scores and a total HOME score: availability of learning materials, language stimulation, physical environment, parental responsiveness, learning stimulation, modeling of social maturity, variety in experience, and acceptance of the child. The HOME Inventory has been used extensively in research studies, and has well-established psychometric properties. An abbreviated version of the full HOME assessment (HOME-SF) had been used to demonstrate the relationship between home environment and obesity risk in children. Increased cognitive enrichment in the home assessed using the HOME-SF is associated with lower obesity rates, and the home environment has been shown to interact with food reinforcement to predict weight loss in older

children. Observers blind to group status will be trained to complete the HOME by interviewing parents and observing parent-infant interactions in the laboratory. We have shown high inter-rater reliability of the lab version of the IT-HOME (intra-class correlations of 0.88 to 0.98).⁹⁰

During mandated social distancing, this will be done virtually via ZOOM.

h) Infant Behavior Questionnaires-Revised (IBQ-R)

This questionnaire is used to measure temperament in infants between the ages of 3 and 12 months. It is one of the most widely used parent-report measures of infant temperament, which has good internal consistency, reliability, and inter-rater reliability between mothers and fathers. Parents will be asked to rate the frequency of specific temperament-related behaviors observed over the past week (or 2 weeks). The IBQ-R assesses the following domains: activity level, distress to limitations, approach, fear, duration of orienting, smiling and laughter, vocal reactivity, sadness, perceptual sensitivity, high-intensity pleasure, low-intensity pleasure, cuddliness, soothability, rate of recovery from distress, and arousal. We previously showed that high food reinforcement is significantly associated with lower scores of cuddliness ($p = 0.03$) and rate of recovery from distress and arousal ($p = 0.015$) (unpublished). Anzman-Frasca and colleagues demonstrated that infant temperament measures moderated the effect of obesity interventions during infancy.

g) Parental Reinforcing Value of Food and Activities Questionnaires

The food choice questionnaire will be used to measure the reinforcing value of food and non-food alternatives of the participating parent at baseline, 3-m, 6-m, 12-m, and 24-m. This questionnaire has been validated against the standard concurrent schedule laboratory task, and has been used with children to study the relationship between child and parent relative reinforcing value of food

. The questionnaire involves asking participants how much work they would do on 3 choice trials. The amount of work (i.e., button presses on a handheld counter) to earn snack foods increases with each choice, but the work required to obtain the alternative reinforcer, which is 10 min of watching a DVD, does not change. The same alternative, videos, is used for all choices so a common metric can be used to quantify all reinforcers. The snack food or alternative reinforcer choice begins at 20 button presses on the first trial, and responding increases by 20 presses on each successive trial for the snack food, with 640 presses required to obtain snack food on the last trial. The questionnaire will be used to assess reinforcing value of 1 out of 6 options of highly palatable, high energy-dense snack food that adult participants have chosen in previous studies and 2 non-food alternatives, which will include 1 physical activity and 1 sedentary leisure time activity, also chosen for a list of possibilities by the participant. Based on our experience using this questionnaire to test multiple reinforcing options in adults, we estimate 3 options would take

approximately 10 minutes. Since we will be including single parent families, we will only assess parental relative reinforcing value for one parent. The focus of data collection will likely be on the mother, as she is more likely to bring in the child than the father, and data suggest that maternal pre-pregnancy BMI is strongly associated with infant's weight. There is only one study on the relationship between parental and child food reinforcement, and this study focused primarily on maternal food reinforcement. There is no research on the relationship between parental and infant food reinforcement

i) Block Food Frequency Questionnaires (FFQ)

An extensively studied and validated paper and pencil version of Block FFQ will be used to assess parent's usual food intake at baseline, 3-m, 6-m, 12-m, 24-m, and 2-4 years old. It will take approximately 30 minutes for the caregiver to complete. There are approximately 110 food items in the questionnaire designed to estimate usual and customary intake of a wide range of nutrients and food groups. Individual portion size is used for each food, and pictures are given to enhance the accuracy of amount consumed. The food list of this questionnaire was developed from NHANES 1999-2002 dietary recall data, and the nutrient database was developed from the USDA Food and Nutrient Database.

j) Infant Daily Health Survey

The Infant Daily health Survey, completed by the participating parent, provides information about the infants' current health and emotional status, including information about medications the infant is taking and the infants' level of fussiness.

h) Child Health and Medical Care Questionnaire

This questionnaire will provide information about the child's current health and medical information; this includes questions about any new mental or medical diagnosis or any developmental delays.

i) Effortful control tasks

Effortful control is a measure of inhibitory control and impulsivity in children and toddlers. For the three-year old children, seven tasks will be used to measure effortful control. All tasks will be video-recorded for scoring. (Kochanska, Murray, Jacques, Koenig, & Vandegeest, 1996).

- Snack Delay. Children will be asked to wait for the experimenter to ring a bell before retrieving an M&M (or other candy/snack, based on preference) from under a glass cup. Four trials will consist of different delays (e.g. 10, 20, 30, and 15 seconds) over 4 trials. At each delay's half-way point, the experimenter will lift the bell, but not ring it. Children will be able to eat the M&M during/after each trial.

- Lab Gift. Children will be asked to face away from an experimenter wrapping a gift for approximately 1 minute. Peeking latency will be scored. Children will be provided the gift after waiting.
- Home Gift. Children will be asked to close their eyes/wear an eye mask while the experimenter wraps a gift for approximately 1 minute. Peeking, removing and adjusting the blindfold will be scored for latency. Children will be able to take the gift home. Gifts will consist of age-appropriate, inexpensive toys (e.g. ball, etc).
- Turtle-and-Rabbit. Children will be asked to move three dolls/figures (human, turtle, rabbit) around a path on a board for about 2 trials. Children will be asked to move the turtle slowly and the rabbit quickly and the human at a normal pace.
- Tower. Children will be asked to take turns with the experimenter while building a block tower using approximately 20 blocks. The experimenter will wait for their turn until the child signals that it is the experimenter's turn.
- Whisper. Children will be asked to whisper the names of cartoon characters (about 10 trials). Characters may include Mickey mouse, Minnie mouse and Paw patrol, or other age-appropriate media that children should be familiar with.
- Prize in a box. Children will be asked not to open a clear box that contains a desirable toy for 2 minutes and time touching, looking at box, and signs of frustration will be coded.
- High Chair. Children will be place in a high chair for approximately 5 minutes with no available toys. Frustration, whining, and self-soothing behaviors will be coded.

j) Temperament questionnaire

The Early childhood behavior questionnaire and the children's behavior questionnaire (Putnam, Gartstein, & Rothbart, 2006; Rothbart, Ahadi, Hershey, & Fisher, 2001) will be used to measure up to 18 temperament dimensions including; discomfort, fear, frustration, high intensity pleasure, impulsivity, inhibitory control, low intensity pleasure, motor activation, perceptual sensitivity, positive anticipation, sadness, shyness, sociability, and soothability. Parents will complete the age appropriate questionnaire (ECBQ 18 – 36 months, CBQ 3 – 5 years) of up to 201 items.

k) Skinfold Thickness

A practical clinical tool used to assess adiposity. This will be measured along with height and weight at the child's appointment for 2-4 years old.

l) Measurement of Ad Libitum food intake for 2-4-year olds.

Age appropriate food will be provided to the child to be able to eat or not eat, whatever they choose, for a time limit of 10-15 minutes.

m) Music/Play Survey

Surveys are given during time of social distancing due to COVID-19 in order to understand what music/play is being done at the home.

n) Perceived Stress Scale

This survey is given during times of social distancing due to COVID-19 in order to understand any stressors the family may be under. It can be given out periodically based on the duration of social distancing.

10.3 List any instruments or measurement tools used to collect data (e.g. questionnaire, interview guide, validated instrument, data collection form).

Include copies of these documents with your submission.

Response:

All documents will be attached along with this protocol submission.

10.4 Describe any source records that will be used to collect data about subjects (e.g. school records, electronic medical records).

Response:

N/A, no source records will be used.

10.5 Indicate whether or not **individual subject results, such as results of investigational diagnostic tests, genetic tests, or incidental findings will be shared with subjects or others (e.g., the subject's primary care physician) and if so, describe how these will be shared.**

Response:

N/A, individual subject results will not be shared.

10.6 Indicate whether or not **study results will be shared with subjects or others, and if so, describe how these will be shared.**

Response:

Study results will not be shared with subjects.

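### For children still nursing, breast milk is derived as 600 mL/day less other milk, with no upper age and no floor at zero, although follow-up recalls fall at about 12 to 39 months

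*Combined protocol and SAP*

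**What the plan says.** Section 10.2 f (Infant Diet and Energy intake) measures diet by three 24-hour telephone recalls. The outcome is defined by this sentence: "We will calculate the average daily energy intake by averaging the three 24-hour energy intakes".

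Breast milk is not measured by volume, so the plan derives it:

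- Sole milk, from 7 months of age with no upper limit stated: "we will assume an intake of 600 mL per day as the quantity of breast milk for those being fed only breast milk". The contrast with the next rule shows that this means children whose only milk is breast milk; they may also eat solid food.
- Mixed milk: the volume of formula or cow's milk "will be subtracted from 600 mL for infants who consume both breast milk and other milk products".
- Feed duration: "interviewers will document the duration of each feeding in minutes". No later sentence says how the minutes enter the volume.
- Review: "A dietetics professional will review all 24-hour recalls for missing foods, unrealistic quantities reported", as well as supplement use and breastfeeding status.

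Section 5.1 gives entry ages of 9 to 15 months. Section 10.1 places the follow-up diet interviews at 3, 6, 12 and 24 months, and the table in Section 10.2 also marks a visit at 2 to 4 years. Section 2.1 names dietary intake as the secondary outcome. Sections 1.1 and 1.2 give it its own aim (1a) and a hypothesis of lower daily energy intake with music. Section 18.1 compares the groups on it at each visit and names no sensitivity analysis for breastfed children.

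**The concern.** One constant serves children from late infancy to over three years, with no age step. A toddler who nurses once a day and drinks no other milk is credited with the same 600 mL as a child who nurses often. For a child who takes both kinds of milk, the derived part is whatever brings the total to 600 mL, so the rule removes real differences in milk volume among nursing children. Nothing stops the derived part from falling below zero.

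At stake is the accuracy of daily energy intake, the only stated secondary outcome. The rule can add error to it, hide real differences in milk intake, and let the date of weaning move a child's recorded energy by an amount unrelated to what was drunk. Because Section 18.1 analyses change over time, such steps enter the outcome directly.

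**Working it through.** No figure in the plan depends on this rule, so there is none to reproduce. The sample size in Section 18.2 rests on FRR and zWFL. The check is to apply the rule as written.

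**Ages at the recalls.** Entry age (9 to 15 months, Section 5.1) plus visit month (Section 10.1):

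| Visit | Age (months) |
|---|---|
| Baseline | 9-15 |
| 3 months | 12-18 |
| 6 months | 15-21 |
| 12 months | 21-27 |
| 24 months | 33-39 |

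Every recall after randomization in this schedule is at about 12 months or older.

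**Total milk.** Let M be formula or cow's milk in mL on a day with any nursing. The rule gives breast milk B = 600 - M. Total milk is M + B = M + (600 - M) = 600 mL for every value of M, including M = 0. Energy can still vary with the type of milk, but total volume cannot.

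**Negative volumes.** B is below zero whenever M exceeds 600. The documents give no energy density for breast milk; I assume 0.60 to 0.75 kcal/mL.

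| M (mL) | B as written (mL) | B with floor (mL) | False deduction that day (kcal) |
|---|---|---|---|
| 480 | 120 | 120 | 0 |
| 600 | 0 | 0 | 0 |
| 720 | -120 | 0 | 72-90 |
| 840 | -240 | 0 | 144-180 |
| 960 | -360 | 0 | 216-270 |

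If one of the three recall days is affected, the three-day mean is too low by 120 x 0.60 / 3 = 24 to 120 x 0.75 / 3 = 30 kcal at 720 mL, and by 360 x 0.60 / 3 = 72 to 360 x 0.75 / 3 = 90 kcal at 960 mL.

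**Error when breast milk is the only milk.** Error = (600 - true volume) x density. The true volume is not in the documents, so I show a range:

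| Assumed true volume (mL) | Overstatement (kcal/day) |
|---|---|
| 0 (limit) | 360-450 |
| 100 | 300-375 |
| 200 | 240-300 |
| 300 | 180-225 |
| 400 | 120-150 |
| 600 | 0 |

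Above 600 mL the sign reverses and intake is understated.

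**Step at weaning.** A child with 200 mL of cow's milk who nurses once is credited with 600 - 200 = 400 mL of breast milk. When nursing stops, the credit falls to zero, a recorded drop of 400 x 0.60 = 240 to 400 x 0.75 = 300 kcal/day, however little was drunk at the breast.

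**Group means.** The shift in an arm's mean is the share of children nursing times their mean error. The documents give no share. If the mean error per nursing child is the same in both arms, the shift in the group difference is the difference in shares times that error. With equal shares it is 0. With an assumed 10-point difference and a true volume of 300 mL it is 0.10 x 180 = 18 to 0.10 x 225 = 22.5 kcal/day; at the limiting error it is 0.10 x 360 = 36 to 0.10 x 450 = 45 kcal/day.

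**The case against.** The strongest case on the other side has five parts.

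- *The rule does not reach every child.* This stands. The full 600 mL goes only to children whose sole milk is breast milk, mixed feeders get the remainder, and weaned children are untouched. A reader might infer a fault in the whole sample; the text does not support that.
- *The rule may not cover toddlers.* It speaks of infants, and Section 10.1 separately uses the word toddler for the follow-up task. But the table in Section 10.2 labels the diet row as infant at all visits, so usage is loose. If toddlers are outside the rule, the plan has no breast-milk rule for many of the follow-up recalls, which also needs repair.
- *A negative volume would not be kept.* A negative amount consumed has no meaning, and a dietetics professional reviews every recall. The review might catch such cases, and the plan does not say that negatives would be retained. But the review is written for reported quantities, the breast-milk volume is derived, and no correction rule is given.
- *The rule is the same in both arms.* This stands against a claim of bias. A shift between arms needs nursing or other-milk intake to differ by arm, and the documents propose no effect of music classes on weaning. Equal use does not remove the added error or restore the lost differences in milk volume.
- *Minutes are a poor guide to volume.* The documents give no conversion and show no gain in accuracy. This limits the remedy but does not justify a fixed total.

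**Conclusion.** The point holds for children still nursing. The written rule has no upper age and no floor, fixes total milk at 600 mL, and yields a negative volume above 600 mL of other milk. These follow from the text and need no outside figure.

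The size of the error is conditional. At an assumed 0.60 to 0.75 kcal/mL, a child whose only milk is breast milk is overstated by anything from 0 to 360-450 kcal/day for true intakes of 0 to 600 mL, and understated beyond that. The effect on group means depends on how many children nurse at each visit and may be small.

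Two stronger readings are tempting. One is that energy intake is badly misstated; the documents give no true volume, energy density or nursing prevalence, so this cannot be shown. The other is to compare the per-child error with the standardized effect of 0.667 in Section 18.2. That figure was planned for zWFL change, no effect size or SD is given for energy intake, and an error in one child is not a difference between group means.

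FRR, zWFL, the home environment score and the sample size are unaffected. The point still deserves action, because a stated rule can give wrong values for the sole secondary outcome and the repair is cheap.

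**What to change.** In Section 10.2 f, with a matching line in Section 18.1:

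1. Set the derived volume to max(0, 600 - other milk). This removes negative values; total milk then becomes the larger of 600 mL and the other milk, so the floor alone does not cure the fixed total.
2. State the age range to which 600 mL applies. Above it, derive volume from the number and minutes of feeds already recorded, using one conversion fixed before the groups are compared.
3. Add a sensitivity analysis of energy intake that excludes recalls with any breast milk, and state whether the single day or the whole visit is dropped.

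The cost is a few lines of text and a small change in nutrient data processing, with no new data collection. There are two downsides. The conversion from minutes to volume is approximate. The exclusion conditions on a behaviour that occurs after randomization, so that analysis should remain supportive and not replace the main comparison.
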